### Screening visit (optional):

- 1) Consenting and confirmation of inclusion & exclusion criteria
- 2) Identification of the target area to be treated with NANODOX® and digital picture of the targeted lesion. The picture will not include subjects' identifiers (e.g. facial features, tattoo, ect)
- 3) possible washout period (topical only in the chosen area – treatment and biopsy sites)
- 4) scheduling visit 1

### Visit 1 (Day 0):

- 1) Consenting and confirmation of inclusion & exclusion criteria
- 2) General History and Physical Exam (including review of concomitant medications)
- 3) Urine Pregnancy test for woman of childbearing potential. Counseling on acceptable birth control measures to use throughout treatment period (28 days) and until 30 days after stopping study drug
- 4) Questionnaire to clinically characterize AD
- 5) Clinical score for atopic dermatitis
- 6) Identification of the target area to be treated with NANODOX® and skin biopsy locations. Arms will be the preferable areas if lesions are present, otherwise trunk or lower extremity
- 7) Digital pictures of the target area and area used for biopsy
- 8) Non-invasive skin barrier Measurements: TransEpidermal Water Loss (TEWL). Optional: pH and Stratum Corneum (SC) hydration measurements may also be performed
- 9) Repeated tape strippings (0, 5, 10, 15 tape-strippings with Cuderm™ tape) of non-lesional and lesional locations from treated area will be collected as part of the TEWL assessment and to assess for SC cohesion/integrity (rate of change in TEWL with repeated strippings).

Serial measurements of TEWL will be performed after tape stripping as previously describedxiii. This will also allow collecting proteins (eluded from the tape) for proteases activity assessment.

- 10) Skin swab
- 11) Optional Skin biopsy (5 mm punch) of a representative skin in the same anatomical area or symmetrical, avoiding the area that will be treated. This biopsy may be performed on D28 at the same time as the post treatment biopsy.
- 12) Venous blood draw to monitor AD biomarkers
- 13) Dispense NANODOX® for two following weeks (14 +/- 2 monodose packages)
  - Subjects will be instructed to keep the NANODOX refrigerated at + 4C; subjects will be provided a cooler and ice packs keep the products refrigerated during transport.
- 13) Provide instructions to complete at home diary.
- 14) Provide date of Visit 2 and “morning of appointment” instructions

**Visit 2 (Day 14 +/-2):**

- 1) Review subject diary and address any questions, concerns, or missed doses
- 2) Questionnaire to clinically characterize AD, review of medications and possible SE
- 2) Clinical score for atopic dermatitis
- 3) Digital pictures of the targeted area
- 4) Non-invasive skin barrier Measurements: transepidermal water loss. Optional: pH and SC hydration measurements may also be performed.
- 5) Repeated tape strippings (0, 5, 10, 15 tape-strippings with Cuderm™ tape)
- 6) Dispense NANODOX® for two following weeks (14 +/-2 monodose packages)
- 7) Suture removal at pre-treatment biopsy site, if applicable
- 8) Review Diary instructions
- 9) Provide date of Visit 3 and “morning of appointment” instructions

In case of complete resolution of the treated area at V2, post treatment biopsy and swab and Venous blood draw will be performed at this visit (instead V3) and patient will only come back for 2 weeks post treatment.

**Visit 3 (Day 28 +/-2):**

- 1) Review subject diary and address any questions, concerns, or missed doses
- 2) Questionnaire to clinically characterize AD, review of medications and possible SE
- 3) Clinical score for atopic dermatitis
- 4) Digital pictures of the targeted area
- 5) Non-invasive skin barrier Measurements: transepidermal water loss. pH and SC hydration measurements may also be performed.
- 6) Repeated tape strippings (0, 5, 10, 15 tape-strippings with Cuderm™ tape)
- 7) Skin swab of treatment area
- 8) Optional skin biopsy (5 mm punch) from treatment site and non-treatment site if not performed at Day 1 visit.
- 9) Venous blood draw
- 10) Provide date of Visit 4 and “morning of appointment” instructions

**Visit 4 (Day 42 +/-5):**

- 1) Questionnaire to clinically characterize AD, review of medications and possible SE
- 2) Clinical score for atopic dermatitis
- 3) Take digital pictures of the targeted area
- 4) Non-invasive skin barrier Measurements: transepidermal water loss. pH and SC hydration measurements may also be performed.
- 5) Repeated tape strippings (0, 5, 10,15 tape-strippings with Cuderm™ tape)
- 6) Suture removal at biopsy site(s)

**Study procedures & methods**

- **Disease status assessment:** **1)** Investigator Global Assessment (IGA), which will provide information of the overall disease (four point scale: clear, mild, moderate, severe) and it is the score requested by FDA for clinical study and **2)** Eczema Area and Severity Index (EASI), a well-accepted and validated scoring system for general disease activityxiv. It is the sum of the intensity scores (0 to 3) for four signs: erythema, induration, excoriation, lichenification and it is recorded for targeted treatment areas as well as four regions of the body (i.e., head, trunk, lower and upper extremities). Data will be reported as percent change in EASI score from baseline and each visit. Proportion of participants achieving EASI50 and EASI75 will be determined at each study timepoints. The presence or absence of skin irritation (e.g. macular/papular eruption), redness, atrophy and telangiectasia will be noted at each study visit.  
**3)** The pruritus intensity will be assessed using the 5-D Pruritus Scale. The pruritus categorical scale is a 4-point scale commonly used in clinical studies of AD and has less of a “middling” effectxv The scale is rated as follows: 0: absence of pruritus; 1: mild, pruritus (occasional slight itching/scratching); 2: moderate pruritus (constant or intermittent itching/scratching that does not disturb sleep) and 3: severe pruritus (bothersome itching/scratching that disturbs sleep).
- **Digital pictures:** A digital picture will be taken with a dedicated digital camera. The pictures will be labeled with the subject’s study ID and date. Pictures will not include identifying information (e.g. facial features, tattoo, etc). Pictures will be taken at a distance for easy identification of the anatomical area and closer to better capture clinical changes. Digital photographs will be used to record the location and monitor the size of target lesions. Quantification of change in size will be obtained using Image J software.  
At conclusion of the study, two trained physicians/dermatologists will be asked to score clinical pictures (0-4 scale, clear, mild, moderate, severe) in a blind fashion (*i.e.*, pictures will be de-identified and presented randomly/ not in chronologic order). This would allow to objectively confirm the clinical score taken during the study.
- **Skin swab:** Skin swabs will be collected for microbiologic analysis to obtain a semi-quantification of skin bacteria pool, including *S. aureus* spp. and to determine antibiotic sensitivity. Skin swabs are performed by swiping and rolling a sterile cotton-tipped applicator 4-5 times across the target area. Swabs will be obtained from NanoDOX® Hydrogel sites pre and post treatment and may be repeated as needed to monitor

bacteria growth during study. The microbiology assay will be run by the Clinical microbiology laboratory at the University of Florida (Rocky Point Lab).

- **Optional Skin biopsy:** One skin biopsy sample (5 mm  $\approx$  pencil eraser size) will be obtained if possible within 4 cm from the treatment area or on the contralateral side. Second biopsy will be obtained from the treatment area post-treatment. Biopsy will be performed after injecting a local anesthetic (Lidocaine +/- epinephrine) to minimize pain and bleeding. The biopsy will consist of removing a piece of skin with a sterile 5-mm skin biopsy punch. At the biopsy site one or two sutures will be placed to ensure better healing, minimize blood loss and to provide a more aesthetic scar formation. A pressure bandage will be applied to the biopsy site to minimize the risk of bleeding and infection. We will provide each subject with a wound care instruction sheet.

Each biopsy will be used for analysis of proinflammatory cytokines (TSLP, IL33, TNF $\alpha$ , IL-1b, and IL-6) and epidermal barrier related protein (e.g. filaggrin, loricrin, claudin1, S100A7) as well as proteases activity (MMPs, elastase) that are typically upregulated in inflammatory skin. This will be done in collaboration with [name] (Professor of Obstetrics/Gynecology & Ophthalmology at the University of Florida, co-PI in the study). It is our hypothesis that NanoDOX $\text{\textcircled{R}}$  Hydrogel by reducing the proteases activity in the epidermis will enhance the integrity of epidermal barrier structure. Secondly, we will evaluate changes in inflammatory (and pro-inflammatory) pathways downstream to proteases activity before and after treatment with NanoDOX $\text{\textcircled{R}}$  Hydrogel. We expect that normalization of molecular pattern parallels clinical improvement (and restore of skin barrier integrity).

- **Tape stripping for proteases activity measurements:** the most superficial layers of the skin will be collected by tape stripping using D-squame (D-squame $\text{\textcircled{R}}$ , CuDerm, Dallas TX, USA – **Figure 2**). This is a well-established method used in clinical research to gently perturb the skin barrier. The first tape will be discarded to eliminate dirt and remnants of skin products. Each tape will be gently pressed against the skin with standardized pressure for 10 seconds (sec) using a standardized pressurizer (D500–D-squame $\text{\textcircled{R}}$  pressure instrument, CuDerm, Dallas, TX, USA – **Figure 2**). Non-lesional skin samples will be collected from the volar side of the forearm and lesional skin samples will be collected from an easily accessible area, such as arms or lower legs.

All subjects will have 20 consecutive tapes collected from lesional skin and 20 consecutive tapes from non-lesional skin. Once the tapes have been collected, as part of this study, we will test different methods to elute the skin proteins from the tapes.

The corneocytes (cells in the most superficial layer of the skin) or their cellular contents that adhere to the discs must be released from the adhesive coating for subsequent analytical steps. So far several groups were able to use this non-invasive method to analyze for the presence of biomolecules, drugs and other cellular constituents.

- **Skin barrier measurements:** Transepidermal water loss/TEWL, +/- pH and SC hydration measurements will be obtained on treatment area at a non-lesional site and on a site of inflammation. For each of the specific measurements, a probe will be gently applied on the skin surface for few (up to 30) seconds. We will perform all measurements in a climate-controlled examination room with temperatures ranging 20-22 $^{\circ}$ C and consistent humidity (preferably 40%). The patient must be very comfortable in

the room in which they are being tested to ensure that perspiration due to stress or acclimatization does not alter the TEWL. TEWL will be measured at baseline and after tapestripping. SC hydration and surface pH will be assessed on non-lesional and lesional skin using the Corneometer® CM825 and Skin-pH-Meter® PH 905, respectively (Courage and Khazaka Electronic GmbH, Kohn GE – **Figure 1**). TEWL will be assessed using the AquaFlux (Biox, London UK). These measurements should provide data to determine if the treatment has an effect on skin barrier integrity.

- **Venous blood sample:** (4 ml) will be obtained to evaluate biomarkers of disease severity. 4mLs will be collected into a redtop serum blood collection tube and allowed to clot at room temperature for minimum of 30 minutes. Blood will be spanned down and serum pipetted into Eppendorf tubes to be stored in -80°C. Tubes will be labeled with study subject ID, data and Visit number, not subject identifying information Tubes will be stored in [name] laboratory for measurement of Th2 biomarkers (markers of disease severity), including serum total IgE and TARC/CCL17.

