**3. METHODS AND PROCEDURES**

**Study Design.** We will perform a 6 weeks, pilot, investigator-initiated, single-center, open-label clinical study to determine the effect of NANODOX® 1% hydrogel in adult AD patients. The study will be conducted in the UF Health Dermatology Department - Springhill.

Subjects that voluntarily agreed to participate will be consented and enrolled in the study. Qualified subjects will be required to come to UF Dermatology Clinic for at least four visits, approximately 2 weeks apart, with an optional pre-screening (up to 28 days +/- 2 prior to V1) visit if washout is needed and/or to allow subjects to be enrolled in pre-established enrollment dates. Each visit will last approximately 30-60 minutes.

Subjects will be asked to apply NanoDOX® Hydrogel 1% once daily at bedtime for total of four weeks (or until complete clearance) on the chosen target eczematous and adjoining clinically normal (perilesional) area (to cover an area of the size of an index card). NanoDOX® Hydrogel 1% will be provided to the patient in single dose package containing 1.5 cc of hydrogel (equal to 15mg Doxycycline) which is enough to cover a skin area of the size of an index card. Alchem will provide drug for the study at no cost. Of note, for systemic use doxycycline is used at concentration from 100 mg (antimicrobial) twice daily to 40 mg (anti-inflammatory) daily for periods ranging from 14 days to several months. We included non-lesional/perilesional skin to evaluate the safety (e.g. irritant or toxic effects) of the compound on atopic skin, as those subjects have a lower irritancy threshold as is compared to non-atopic subjectsxii. Also, skin barrier impairment (e.g. increase water loss & increase pH) can be already detected in normal

appearing skin in AD subjects. It is our hypothesis that by normalizing the proteases activities, treatment with NanoDOX® Hydrogel will normalize skin barrier integrity.

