## **5. DATA ANALYSIS AND DATA MONITORING**

### **Primary Outcomes:**

1. Assessment of safety and tolerability of NanoDOX® Hydrogel in AD subjects on lesional and non-lesional (clinically normal appearing) skin, including pain and dermatologic/skin toxicity (incidence, severity, frequency, duration and causality) in lesional skin at target site (NanoDOX® Hydrogel). 2. Improvements rate of IGA and EASI score in lesional skin treated with NanoDOX® Hydrogel before and after treatment. We will quantify clinical improvement as: IGA (0-4) fold improvement from baseline; percent of subjects reaching EASI50 (50% improvement over baseline) or EASI75 (75% improvement over baseline) at each time point post treatment (V2 and V4). 3. Objective Clinical improvement based on digital photography scoring (0-4 scale and size of active lesion), measured as fold improvement over baseline at each time point (V2 and V4).

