### **Secondary Outcomes:**

1. Improvements of itch score (0-5 scale) in lesional skin, before and after treatment at each time point. 2. Will evaluate Staphylococcal Aureus rate of colonization (positive or negative), difference in number of growth (0 to 3+++ ) and antibiotic sensitivity pre and post treatment. Doxycycline could have an effect on AD lesions just by reducing the Staphylococcal Aureus colonization. By integrating these findings with clinical outcomes, drug penetration and molecular changes we will be able to start to address this question. 3. Improvement of barrier function in non-lesional (normal appearing) and lesional skin pre and post treatment (V1 to V3). We will expect that clinical improvement parallels with improvement of barrier function, such as reduced TEWL, increased stratum corneum hydration and reduced pH in active treatment areas. On the other hand, worsening of the measurement will suggest damaging effect of the treatment on the skin, which could be indication of subclinical irritation induced by the treatment and/or vehicle.

The purpose of this study is a proof of concept. We are adopting a similar strategy to Phase II cancer trials that seek a clinically significant response. Using exact binomial methods, we shall obtain point and interval estimates for the fraction of subjects who respond as (a) At least EASI 50% by visit 2 or 4 and (b) At least EASI 75% by visit 2 or 4. We shall also tabulate the IGA score from baseline to visit 4. We would consider 6 or more responses (a) in 15 subjects as promising. The probability of declaring a promising result when the true response rate is 60% or higher is over 96% (power).

Side effects and baseline characteristics will be tabulated qualitatively. The blinded pre-vs post evaluation will be analyzed for IGA scores by the Wilcoxon sign-rank test.

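### Primary outcome 2 needs an IGA of the treated lesion, but the only clinic IGA the protocol defines rates the overall disease

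*Combined protocol and SAP*

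**What the plan says.** Under Study procedures & methods (Disease status assessment), the first score is the "Investigator Global Assessment (IGA), which will provide information of the overall disease". The second is EASI, of which the same paragraph says that "it is recorded for targeted treatment areas as well as four regions of the body". So EASI has a target-area version and IGA does not.

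Section 5, Primary Outcomes, item 2, then asks for "Improvements rate of IGA and EASI score in lesional skin treated with NanoDOX® Hydrogel before and after treatment", with IGA expressed as fold improvement from baseline and EASI as the percentage reaching EASI50 or EASI75 at V2 and V4. The analysis text at the end of Secondary Outcomes adds a tabulation of IGA from baseline to visit 4. It also sets the response rule: at least 6 of 15 subjects with "At least EASI 50% by visit 2 or 4".

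Under Study Design (section 3), the gel is applied to the chosen lesion and adjoining normal skin so as "to cover an area of the size of an index card". Subjects may keep other topical treatment outside that area at a stable dose. The study is open-label with a single arm.

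**The concern.** A named primary outcome and the instrument meant to measure it refer to different things: the outcome to one treated lesion, the instrument to the whole patient. A site that follows the methods paragraph will record one overall grade per visit. That grade will then be reported as if it described the treated skin.

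The error could go either way. A lesion can clear while the overall grade stays put because the untreated skin is unchanged. The overall grade can also improve through the natural course of disease elsewhere, and without a control arm nothing in the design would separate that from an effect of the gel.

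**Working it through.** **The plan's own figure.** Inputs from the end of Secondary Outcomes: n = 15, at least 6 responders, true response rate 60%. With X binomial(15, 0.60), P(X ≥ 6) = 1 − P(X ≤ 5) = 1 − 0.0338 = 0.9662. This agrees with the stated power of over 96%. The rule counts EASI responses only, so no choice of IGA definition enters the calculation.

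**Following IGA through the protocol.**

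| Place | What is scored | Site of the score |
|---|---|---|
| Disease status assessment | IGA, by the investigator | Overall disease |
| Visit 1 to Visit 4 lists | A clinical AD score, instrument not named | Not stated |
| Stopping Criteria | A clinician's dermatological score, instrument not named | Target lesion area |
| Digital pictures, read with the visit lists | Blinded severity score by two physicians | Target-area pictures |
| Primary Outcomes, item 2 | IGA, fold improvement | Treated lesional skin |
| Primary Outcomes, item 3 | Photograph score and lesion size | Photographed lesion |
| End of Secondary Outcomes | IGA tabulated to visit 4 | Not stated |
| End of Secondary Outcomes | Wilcoxon test of IGA scores from the blinded evaluation | Target-area pictures |

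The first row is the only definition of a clinic IGA, and it does not match the site in item 2. The visit lists do not fill the gap. The stopping rule shows that some clinician-rated lesion score was intended, but it does not say which, and target-area EASI would satisfy it. The photograph score is at the right level, but it is a separate primary outcome (item 3), and item 2 does not refer to it.

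**How far an overall grade could follow the gel.** The gel can change the overall grade only through the treated lesion. Suppose that lesion and overall disease are both moderate at baseline, the lesion clears, and the rest is unchanged. A lesion IGA moves from moderate to clear, while the overall IGA may remain moderate. The two agree only where disease is largely confined to the target. The documents do not give the lesion's share of each subject's disease, so the loss of sensitivity cannot be put as a number. Its direction is clear: the more disease outside the card, the less the overall grade says about the gel.

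**The case against.** The strongest reply is that lesion-level intent runs through the document. Item 2 says treated lesional skin, the stopping rule speaks of the target lesion, and the photographs are of the target area. The single IGA test is run on the blinded photograph scores, the clinic IGA is only tabulated, and it has no part in the decision rule. All of this is right, and it limits the consequence. It does not supply a definition: intent in an outcome list does not tell the rater what to grade, and the one instruction the rater has says overall disease.

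A reader might go further and infer that the 6-of-15 rule could be computed on whole-body EASI. The rule's wording, "At least EASI 50% by visit 2 or 4", names no version, and neither does the methods statement on EASI50 and EASI75. The consequence would be large. If the lesion carries a share f of the whole-body score, clearing it lowers that score by at most f, so whole-body EASI50 from the gel alone needs f of at least 50%. As an illustration, assume a 60% lesion response, count every responder as cleared, and let q be the assumed share of subjects with disease that confined. The response rate is 0.6 × q. At q = 20% the rate is 12% and P(X ≥ 6) is 0.6%. At q = 50% the rate is 30% and P(X ≥ 6) is 27.8%.

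The documents do not support that inference. A target-area EASI is recorded, item 2 ties EASI50 and EASI75 to treated lesional skin at V2 and V4, and the rule in the same section uses the same thresholds and visits. Target-area EASI is the natural reading, and only a missing cross-reference remains.

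Two other tempting statements also fail. One is that the gel cannot move an overall score: it can, up to the lesion's unknown share. The other is that the treated fraction of body surface measures the problem. Share of skin is not share of disease, and EASI is described here as "It is the sum of the intensity scores (0 to 3) for four signs" with no area weighting. Nor can change elsewhere simply be put down to other topical drugs, since these must stay at a stable dose.

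**Conclusion.** The mismatch is real and confined to IGA. As written, the IGA part of primary outcome 2 and the IGA tabulation to visit 4 would report overall disease under the name of the treated lesion. That is one component of one of three primary outcomes, plus one descriptive table. The EASI part of item 2, the photograph outcome, the Wilcoxon test, the 6-of-15 rule and its 96.6% power are untouched.

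The conclusion rests on reading the methods paragraph literally and on subjects having some disease outside the target area. The first is the only definition available. The second is an assumption about extent that the documents neither quantify nor contradict. The correction should be made before data collection, because a lesion grade not recorded at the visit cannot be recovered from an overall grade.

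**What to change.** In Disease status assessment, Primary Outcomes item 2 and the analysis text at the end of Secondary Outcomes, define the IGA as a rating of the target lesion made by the investigator at each visit. State its grades, since the methods list four and item 2 uses a 0-4 range. Keep overall IGA for eligibility and description, labelled as such.

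The alternative is to name the blinded photograph score as the IGA for item 2 and the tabulation. That needs no new rating and is blinded, but the IGA part of item 2 would then largely coincide with item 3, and the text should say so.

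As a cross-reference only, state beside the response rule that responses (a) and (b) use the target-area EASI already recorded, as item 2 implies.

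The cost is wording in three places and, under the first option, one extra rating per visit of a lesion already examined and photographed. Sample size and stated power do not change.

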## 2. CHARACTERISTICS OF THE RESEARCH POPULATION

**Number of subjects** We intend to have 15, non-pregnant, non-lactating women and men of any race and ethnicity, ages 18 to 65 yrs, who are generally healthy except for atopic dermatitis diagnosed by the US Consensus criteria complete this study. This may require enrolling up to 30 subjects depending on retention rates and dropouts. Patients can have other allergic conditions such as asthma, allergic rhinitis, food allergies, etc. All AD subjects must have

moderate-severe AD as defined at screening by an Eczema Area and Severity Score (EASI)  $\geq$  10.

**Gender of subjects** We will be recruiting both male and female subjects

**Age of subjects** We will be including subjects between the ages of 18 and 65 years.

**Racial and Ethnic Origin** We will not have any restrictions based on racial or ethnic origin. We based our target research population racial and ethnic distribution on the data of the 2000 United States Census for the Alachua Area.

**Vulnerable subjects** We will not be targeting vulnerable subjects, however staff and students of UF and Shands may be enrolled as part of the general population with AD

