### **Inclusion Criteria**

- Male or female, 18 through 65 years of age, inclusive who are generally healthy except for active atopic dermatitis diagnosed by the following criteria.
- **Active Atopic Dermatitis:** Subjects *must have* according to medical records, patient account or by medical exam of the investigator:
  - Pruritus
  - Eczema (acute, subacute, chronic)
  - Chronic or relapsing history

Most subjects *will have* (seen in most cases, adding support to the diagnosis):

- Early age at onset
- Atopy
- Personal and/or family history
- Xerosis

Subjects *may have* (these clinical associations help to suggest the diagnosis of AD but are too nonspecific for defining or detecting AD for research or epidemiological studies):

1. Atypical vascular responses (e.g., facial pallor, white dermographism, delayed blanch response)
  2. Keratosis pilaris/hyperlinear palms/ichthyosis
  3. Ocular/periorbital changes
  4. Other regional findings (e.g., perioral changes/periauricular lesions)
  5. Perifollicular accentuation/lichenification/prurigo lesions
- Moderate to Severe AD: clinical score based on EASI  $\geq$  10 and/or IGA 1-2.
  - If receiving antihistamines, are on a stabilized dose, and expect to maintain this dose throughout the study
  - All female subjects of childbearing potential must have a negative pregnancy test at screening visit and must be on an acceptable methods of contraception from the Screening Visit continuously until 30 days after stopping study drug.

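### The written EASI rule has no area term, region weights or combining rule, so the entry cut-off of 10 and the target EASI50/75 are not those of the index the protocol names

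*Combined protocol and SAP*

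**What the plan says.** All references are to the combined protocol and SAP.

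- **Name of the index** (Study procedures & methods, disease status assessment): "Eczema Area and Severity Index (EASI), a well-accepted and validated scoring system for general disease activity".
- **Scoring rule** (same place): "It is the sum of the intensity scores (0 to 3) for four signs: erythema, induration, excoriation, lichenification".
- **Where it is scored** (same place): "it is recorded for targeted treatment areas as well as four regions of the body (i.e., head, trunk, lower and upper extremities". Nothing says whether these recordings are added, averaged, weighted or kept apart.
- **Entry** (section 2, Number of subjects): subjects must have "moderate-severe AD as defined at screening by an Eczema Area and Severity Score (EASI", with a threshold of at least 10. The Inclusion Criteria open with "Moderate to Severe AD: clinical score based on EASI" and continue "10 and/or IGA 1-2".
- **Outcome** (section 5, Primary Outcomes, item 2): for treated lesional skin, "percent of subjects reaching EASI50 (50% improvement over baseline) or EASI75 (75% improvement over baseline". Item 3 separately covers the photograph score and the size of the active lesion, which Study procedures & methods says is measured with Image J.
- **Decision rule** (statistical paragraph under Secondary Outcomes): "We would consider 6 or more responses (a) in 15 subjects as promising", where response (a) is EASI50 by visit 2 or 4. The stated power is over 96% at a true response rate of 60%.

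**The concern.** The index has area in its name, and the rule written for it has none. This one score defines the moderate-severe population, supplies EASI50 and EASI75 in primary outcome 2, and is the only score in the rule that decides whether the result is promising.

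If site staff follow the text, two things go wrong. The cut-off of 10 is applied to a number on a different scale, and that scale is itself unsettled because the combining rule is missing. Results would also be reported as EASI50 and EASI75 when they are percentage falls in a four-sign intensity sum at one target site. A reader comparing them with other studies would take them for the named index.

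**Working it through.** **1. The plan's own figure.** With n = 15 and 6 or more responders needed, the exact binomial probability at a true rate of 0.60 is P(X ≥ 6) = 0.9662. This reproduces the stated power of over 96%.

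**2. Range of the written score.** Four signs graded 0 to 3 give a maximum of 4 × 3 = 12 at one site.
- One site, or the mean of the regions: 0 to 12.
- Four regions summed: 0 to 4 × 12 = 48.
- Four regions plus the target summed: 0 to 5 × 12 = 60.

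The text does not choose among these.

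**3. What a cut-off of 10 does.** With all four signs at grade g in k summed sites, the score is 4 × g × k.

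| Pattern | Score | Reaches 10? |
|---|---|---|
| All mild (g = 1), regions summed, k = 1 | 4 | No |
| All mild, k = 2 | 8 | No |
| All mild, k = 3 | 12 | Yes |
| All mild, k = 4 | 16 | Yes |
| All mild, one site or mean of regions | 4 | No |
| All moderate (g = 2), one site or mean of regions | 8 | No |

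On the one-site reading, the only grade patterns that reach 10, in any order, are 1,3,3,3; 2,2,3,3; 2,3,3,3; and 3,3,3,3. At least two signs must be severe and none absent. So on one reading the cut-off admits subjects with uniformly mild signs, and on the other it excludes subjects with uniformly moderate signs. Neither fits its label of moderate-severe.

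**4. What the target EASI50 measures.** Primary outcome 2 concerns treated lesional skin, so the response score is taken to be the target score, for which the only rule given is the four-sign sum.
- Signs halve, for example from 8 to 4: (8 − 4)/8 = 50%, a responder.
- Lesion clears: the sum is 0, a 100% fall, a responder.
- Lesion area falls by 50%, 75% or 90% with signs unchanged at 8: (8 − 8)/8 = 0% each time, a non-responder.

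For comparison only, and assuming a score equal to area grade times sign sum, a fall in the area grade to 0.50 or 0.25 of baseline would give falls of 50% and 75%. The documents give no area scale, so this shows direction and not an expected result.

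**5. Would an area term alone mend entry?** Assume, for illustration, area grades of 0 to 6, the same grade A in every region, and region weights summing to 1. An all-mild subject then scores 4 × A: 4, 8, 12, 16, 20 and 24 for A = 1 to 6. Such a subject is excluded at grades 1 and 2 and still admitted from grade 3 upward.

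**The case against.** The strongest reply is that the sentence is shorthand. The protocol names the index, calls it validated and cites a source for it, and no score sheet is in the documents, so staff may in practice score area. That is possible. But the sentence is the only scoring rule given, and it states a different formula from the one the name implies. If staff do score area, the sentence is wrong and needs replacing; if they do not, the score is not the named index.

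The second reply is that keeping intensity and size apart is a legitimate choice for a treated area the size of an index card, and that size already has a place in primary outcome 3. That stands. The objection here is to the label EASI50/75, not to an intensity measure as such.

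Three stronger inferences are tempting, and the documents do not support them:

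- *That the rule admits subjects with all-mild signs.* This needs the regional scores to be added, which the text does not say. Nor is it due to the missing area term alone, as step 5 shows.
- *That EASI50 cannot register a shrinking lesion.* It registers easing signs and full clearance. Only shrinkage at constant intensity goes uncounted.
- *That the 96% power fails.* The calculation takes as given a 60% rate of whatever response is counted, and it is correct. Any reduction would need the share of responders who improve by shrinkage alone, and the documents give no such share.

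**Conclusion.** The point holds as a wrong stated rule, and it should be corrected. The written score has no area term, region weights or combining rule. Its range is 0 to 12 or 0 to 48 (60 if the target is added), so a cut-off of 10 does not carry the meaning it has on the named index. The direction of the entry error depends on the reading: all-mild signs in three regions score 12 if regions are summed, while all-moderate signs score 8 and are excluded on a one-site or mean reading. The target EASI50/75 is an intensity-only measure in which shrinkage at constant intensity counts for nothing toward 6 of 15.

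This rests on following the sentence literally and on reading the response score as the target score. Entry also depends on a separate conflict: section 2 requires an EASI of at least 10, whereas the Inclusion Criteria join that threshold to an IGA range by an and/or. Read as an alternative, the IGA route bypasses the EASI threshold, so correcting the formula alone would not settle who is eligible.

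**What to change.** 1. Replace the scoring sentence in Study procedures & methods. Compute whole-body EASI by the full cited instrument, with its area scores and region weights, and state the formula and range.
2. Apply the entry criterion of at least 10 to that whole-body score only, and reconcile section 2 with the and/or IGA wording in the Inclusion Criteria.
3. Call the four-sign target measure a target sign score. State that the 6-of-15 rule counts a 50% fall in it, and do not report it as EASI50 or EASI75. Amend Primary Outcomes item 2 and the statistical paragraph to match.
4. Report Image J lesion size beside the target sign score. Do not multiply the two into one response score: that would be an ad hoc composite and would make response easier to reach in an uncontrolled, open-label study.
5. The Stopping Criteria refer to a clinical score in the target area without naming it. State which score is meant, so that the renaming leaves no ambiguity; no change to the criterion is proposed here.

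The cost is revised wording in these sections and an area field for each region on the score sheet, with no added visit, procedure or patient. Scoring takes slightly longer, and a few fewer subjects may be eligible.
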